A total of 38 participants were enrolled, with randomisation into two groups (n=17 experimental, n=17 control). Sample size was determined using power analysis for an independent t-test, accounting for a 10% dropout rate.

Statistical Analysis

Data will be analysed using SPSS v25.0. Statistical tests include independent t-tests, paired t-tests, and effect size calculations (Cohen's d, Hedges' g). Significance is set at $p<0.05$.

Ethical Approval

The study was approved by the institutional ethics committee on 27 December 2024 (Nr. SSV6-114). All participants provided written informed consent.

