For secondary analyses, linear regression will be used to explore associations between baseline body fat percentage and changes in adiposity outcomes. Significance will be set at $p < 0.05$.

7. Handling of Missing Data

Missing data will be evaluated for randomness. If $<5\%$ missing, analyses will be conducted using complete cases. If $>5\%$, multiple imputation methods will be considered. Sensitivity analyses will be performed to assess robustness.

8. Interim Analysis

No interim analyses are planned due to the small sample size and short study duration.

9. Statistical Software

All analyses will be conducted using SPSS version 25.0. Supplementary analyses may be performed using R version 4.3 or later.

10. Reporting

Results will be reported in accordance with CONSORT guidelines. Tables and figures will be used to illustrate changes in primary and secondary outcomes. Effect sizes, confidence intervals, and p-values will be reported.

11. Ethical Considerations

All analyses will be performed on de-identified data. Analyses will adhere to ethical standards and respect participant privacy.

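### SAP 7 commits to a missing-data method only below 5% missing and defines no unit, denominator or arm, although the Protocol plans for 10% dropout

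*SAP*

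**What the plan says.** SAP section 7 has two branches: "If $<5\%$ missing, analyses will be conducted using complete cases. If $>5\%$, multiple imputation methods will be considered". Below the threshold the method is fixed. Above it, nothing is fixed. No imputation model is named, and there is no fallback if imputation is considered and rejected. The section also says that missingness will be examined for randomness, and it adds: "Sensitivity analyses will be performed to assess robustness". Those sensitivity analyses are not described. The section does not say whether the percentage refers to women, variables or single values, or what the denominator is. It names no visit and does not mention arm.

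Three other places bear on this:

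- Protocol, Sample Size: "Sample size was determined using power analysis for an independent t-test, accounting for a 10% dropout rate". The same section says "A total of 38 participants were enrolled" and gives 17 women per arm, which makes 34.
- SAP section 4: the primary population is randomised women with a baseline and at least one follow-up measurement, under the label of intention to treat.
- SAP sections 5 and 6: both primary endpoints are changes from baseline to week 4, compared between arms by t-test or Mann-Whitney test without baseline adjustment. Dermal measurements are also planned at week 8.

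**The concern.** The planned dropout is twice the threshold, so the only branch with a definite method covers losses smaller than the Protocol allows for. With samples this small, 5% is a matter of one or two women. A pooled percentage also cannot distinguish balanced losses from losses confined to one arm.

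Two things are at stake. If the open branch applies, the primary method can be settled after outcome data are available, in an open-label trial. If it does not apply, the primary result rests on a complete-case comparison of unadjusted change scores. Change depends on baseline through regression to the mean, so that comparison is biased when loss in one arm is related to baseline severity.

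**Working it through.** **Inputs.** 5% threshold (SAP 7); 10% dropout, 38 enrolled, 17 + 17 = 34 (Protocol, Sample Size); population of women with baseline and at least one follow-up (SAP 4); primary endpoints at week 4, later values at week 8 (SAP 5).

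**The plan's own figure.** 34/0.9 = 37.8, which rounds up to 38. So 38 is consistent with 34 inflated for 10% dropout. But 15 per arm inflated also gives 17 (15/0.9 = 16.7), so 34 could itself contain the allowance. The Protocol does not say which.

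**Where the threshold falls, counting women over all randomised.**

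- n=34: 1/34 = 2.9%, 2/34 = 5.9%.
- n=38: 1/38 = 2.6%, 2/38 = 5.3%.
- By arm: one loss is 1/17 = 5.9% of an arm but only 2.9% of 34. Two losses from one arm (2/17 = 11.8% against 0%) are treated the same as one from each.

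**Reading A: denominator is all randomised.** With independent loss at 10%, P(at least 2) = 1 − 0.9^n − n × 0.1 × 0.9^(n−1).

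- n=34: 1 − 0.028 − 0.105 = 0.867.
- n=38: 1 − 0.018 − 0.077 = 0.905.
- At 5% loss the same formula gives 0.512 and 0.573.

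If the four women between 38 and 34 were lost after randomisation and are counted, 4/38 = 10.5% and the open branch is certain. If they account for the 10% allowance, taking a further 10% off 34 counts it twice.

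**Reading B: denominator is the SAP 4 population.** A woman who leaves before week 4 and does not return has no follow-up, so she is excluded and not counted as missing. A woman who leaves after week 4 already has her primary value. Under monotone dropout the week-4 endpoints therefore have no missing values in this population, whatever the loss. Only a woman with a week-8 but no week-4 value would count. The rule then matters mainly for week-8 endpoints. With 34 randomised and 10% total dropout, P(more than 5% missing at week 8) is 86.7%, 51.2% or 0% if none, half or all of the dropout precedes week 4.

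**Bias of the unadjusted complete-case comparison.** These are assumptions and do not come from the documents: no true effect, 17 per arm, normal data, higher score means worse, and the taped women with the mildest baseline are lost. If their loss raises the taped arm's mean baseline by δ SD, the bias in SD of change is (1−ρ)δ/√(2(1−ρ)) = δ√((1−ρ)/2), where ρ is the baseline-follow-up correlation. Simulation (40,000 trials per cell, two-sided 5% t-test, nominal favourable rate 2.5%) gives:

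| Losses | ρ | Bias favouring taping (SD of change) | False favourable rate |
|---|---|---|---|
| 1 of 17 | 0.5 | 0.057 | 3.7% |
| 1 of 17 | 0.6 | 0.050 | 3.4–3.7% |
| 1 of 17 | 0.8 | 0.035 | 3.1–3.2% |
| 3 of 17 | 0.5 | 0.149 | 6.2% |
| 3 of 17 | 0.6 | 0.13 | 5.5–5.7% |
| 3 of 17 | 0.8 | 0.094 | 4.6% |

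Ranges are the spread over repeated runs. As a check on the three-loss rows, 0.149/0.5 gives δ = 0.298; then 0.298 × √0.2 = 0.133 and 0.298 × √0.1 = 0.094, in agreement.

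- If three losses are only moderately related to baseline (correlation 0.5), the bias is 0.05 to 0.08 SD and the rate 3.2 to 3.9%.
- If the three most severe leave, the bias has the same size against taping and the false favourable rate falls to about 1%.
- With baseline adjustment of the same completers, the bias is within 0.003 SD and the rate 2.4 to 2.7%.

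**The case against.** The strongest reply is that a reader might infer from 10% dropout and a 5% threshold that the primary analysis will usually end in the open branch, with the 87% as a forecast. The documents do not support that. It requires counting women over everyone randomised, which SAP 7 does not say. SAP 4 points the other way for the week-4 endpoints, and 34 may already be net of the dropout allowance. This part of the reply stands, so the 87% and 90% hold only on the first reading.

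A reader might also infer that the second loss changes the primary method. It does not: above 5% the SAP compels no change, it only leaves the choice open. Nor does the SAP say that anyone would compare both results before choosing.

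The bias figures can be challenged too. Three losses are 3/34 = 8.8%, above the threshold, where SAP 7 does not prescribe complete cases. The under-5% branch at n=34 permits one loss, with a rate of 3.1 to 3.7%. If loss were random, all three would be taped women only about 11% of the time. The documents give no reason to expect the mildest women to leave rather than the most severe, or taped women rather than controls. All of this stands, so the figures are illustrations.

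Finally, SAP 7 promises to evaluate randomness and to run sensitivity analyses. Neither closes the gap: no check of randomness is informative with one or two losses, and the sensitivity analyses have no content.

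**Conclusion.** The point holds conditionally. SAP 7 fixes a method only below 5%, leaves unit, denominator and arm undefined, and so allows two readings with different consequences. Over all randomised women, the primary method is left open from the second loss, with probability about 87% (n=34) or 90% (n=38) at 10% independent loss, if the allowance is not already spent. Within the SAP 4 population and under monotone dropout, the primary is an unadjusted complete-case comparison however many women leave, and the threshold gives no protection.

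On the assumed scenarios that comparison is off by about 0.03 to 0.06 SD of change for one selective loss and 0.09 to 0.15 SD for three, with false favourable rates of 3.1–3.7% and 4.6–6.2% against 2.5%. The sign reverses if the most severe leave. It would be wrong to conclude that the 5% switch causes this bias. It comes from comparing completers without baseline adjustment; the switch merely fails to guard against it. Pilot status limits the stakes, but the plan still names two primary endpoints and tests them at 0.05.

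**What to change.** 1. Delete the 5% switch.
2. Reconcile SAP 4 with SAP 7: include every randomised woman with a baseline in the primary analysis, whether or not she has a follow-up value.
3. Fix one primary method in advance, whatever the amount missing: a likelihood-based repeated-measures model with baseline modelled jointly with weeks 4 and 8 (common baseline mean across arms), reporting the week-4 arm difference. Multiple imputation, if fully specified in advance, would also close the gap; the essential features are pre-specification and conditioning on baseline.
4. Report losses by arm and visit, with reasons, over all randomised women, and state where the four women between 38 and 34 were lost.
5. Name the promised sensitivity analysis: shift the unobserved taped-arm changes toward no benefit until the conclusion changes, and report that shift. The model in step 3 handles loss related to observed values; this step addresses loss related to unobserved ones.

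The cost is SAP wording and one standard model (SPSS MIXED) in software the SAP already names. No new data are needed, because week-8 values are already planned. The drawbacks are a slightly more complex model than a t-test and possibly a slightly wider interval.
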